## **11 Reports**

A Non-Interventional Study Report based on the results obtained will be prepared and submitted to Global Research for distribution. The Final Study Report should be available within one year from collection of the last data point, and the participating sites should be informed about the results when the report is finalised.

The definitive closure of this study will occur once all the data of the last patient included in the study has been completed. After closing the database, the statistical analysis shall be carried out and a report submitted, that will be reviewed and approved by the study sponsor and coordinating investigator.

In accordance with current legislation, a copy of the final report shall be submitted to the IECs that have authorised the study, the competent bodies in the autonomous communities where the study is conducted and the AEMPS.

## **12 Publications**

Takeda aims to have the results of this study published.

Takeda has the right to use the data and results for regulatory purposes and for internal presentation within the company and to partners.

All information relating to the study is considered confidential and the property of the sponsor until its publication. It may not be revealed to others without the prior written consent of the sponsor and may not be used for any reason other than for the execution of this study.

Only the sponsor or its representatives may extend the information obtained in this study to physicians and regulatory bodies, unless this is demanded by means of an order.

The results of this study will be published in scientific journals and/or presented at conferences.

The final decision to publish any article/abstract/presentation shall be made by the sponsor.

### **13 Archiving of Study Documentation**

During the course of the study the Site Responsible must as a minimum file the essential documents (Section 3.5), the protocol, any amendments, the list of participating subjects, the written informed consents, the CRFs and the progress reports in the Study Site File. After final database lock the Site Responsible must as a minimum store the list of participating subjects and the signed Informed Consent Forms on site for 5 years. The Site Responsible should store additional study documentation for a longer period of time as required by any local regulations and/or hospital requirement.

**Appendix 1: Brief Pain Inventory (BPI).**

[figure not shown]
CCI

[figure not shown]
CCI

CCI

CCI

**Appendix 3: Karnofsky performance status.**

CCI

[figure not shown]

**Appendix 4: Alberta Breakthrough Pain Assessment Tool.**

[figure not shown]
CCI

[figure not shown]
CCI

CCI

[figure not shown]
CCI

CCI

CCI

CCI

**1. HISTORY OF REVISION (Documentation of changes)**

SECTIONS	VERSION	DATE REVISED	REVISED BY	DESCRIPTION OF CHANGES
6.2., 6.4 and 8.	1.0	22/01/2017	PPD	Request for additional analyses

## 2. INTRODUCTION

This statistical analysis plan (SAP) describes the planned analysis for CARPE-DIO study. In it is described all consideration over study data and are defined the tables, figures and listing (TLFs) that will be presented as result of the study.

Additionally includes definition of the different population and missing data consideration.

The statistical analysis plan will be signed and per protocol dataset will be defined before database lock.

### Table of abbreviations

BCP	Breakthrough Cancer Pain
SD	Standard Deviation
Karnofsky PS	Karnofsky Performance Status
95% CI	95% Confidence Interval
BPI	Brief Pain Inventory

### 3. SYNOPSIS

#### 3.1. Study title

“Characterisation and Epidemiology of Breakthrough Cancer Pain in Spain”

#### 3.2. Study Code

CARPE-DIO Study.

#### 3.4. Design

This is a cross-sectional, non-PAS, non-interventional, epidemiological study. Given the observational and cross-sectional nature of the study, the protocol does not include any interventions with regard to patient follow-up by the investigator.

This study is a ‘non-interventional study’ and will follow the guidelines for GPP. This means that:

- The assignment of a subject to a particular therapeutic strategy is not decided in advance by the study protocol but falls within current practice.
- No additional diagnostic or monitoring procedures shall be applied to the subjects.
- Epidemiological methods shall be used for the analysis of collected data.

### 3.5. Objectives

#### Primary:

- To estimate the prevalence of breakthrough cancer pain in an unselected representative cohort of cancer outpatients with or without pain who attend consultations at Medical Oncology, Hematology, Radiotherapeutic Oncology Departments, Pain Units and Palliative Care Units at participating sites.

The estimated annual prevalence will be calculated relative to the population of cancer patients with or without pain seen in participating practices over one month.

#### Secondary:

- To estimate the annual incidence of patients with breakthrough cancer pain relative to the population of cancer patients with or without pain seen in participating practices over one month.
- To characterize breakthrough pain in patients with cancer pain based on medical history, etiology and pathogenesis, tumour type, location, stage, comorbidities, etc., as well as other clinical characteristics (type of breakthrough pain, number of episodes per day, duration and intensity, and baseline pain management). This information will be collected with the tools used for the clinical assessment of breakthrough pain.
- To assess the prevalence of each of the different causes of pain.
- To determine the percentage of patients who present each of the different profiles/types of breakthrough cancer pain (characterization/classification) and classify them based on the results obtained in the Alberta and BPI questionnaires.
- To determine the percentage of patients who present each of the profiles/types of breakthrough cancer pain and assess possible relationships with demographic characteristics and other clinically significant variables related to the cancer such as diagnosis, pain intensity, comorbidities, etc.
- To assess the quality of life of patients with breakthrough cancer pain and its possible relationship with demographic characteristics and other clinically significant variables related to the cancer or to the breakthrough pain such as etiology, frequency of episodes, pain intensity, time until peak of pain, crisis duration, cause, etc.
- To assess the performance status of patients using the Karnofsky scale in order to know the degree of general wellbeing and ability to cope with activities of daily living presented by the patients studied.

### 3.6. Total number of subjects

It is estimated that more than 10 patients per day attend consultations for cancer in Medical Oncology, Radiotherapeutic Oncology, Hematology and Palliative Care Departments and around 5 patients in Pain Units. Breakthrough cancer Pain (BCP) is a common and incapacitating subtype of pain that affects a percentage of patients with cancer that varies between 40% and 90% according to different publications. Conservatively, it is expected to detect the prevalence in 50% of patients, and it is estimated that at each site a total of approximately 200 patients, or around 13,200 across the 66

## “Characterisation and Epidemiology of Breakthrough Cancer Pain in Spain”

planned sites, will be interviewed on the prevalence of breakthrough cancer pain. This sample will enable us to detect the prevalence of breakthrough pain with a 95% confidence interval and precision of  $\pm 1\%$ .

For the assessment of the secondary objective, i.e., characterizing the breakthrough pain based on etiology, underlying pathology and other clinical characteristics, if it is considered the detection of common characteristics in at least 10% of patients in our population to be representative, it will be necessary to recruit 529 patients in order to detect said characteristics with a 95% confidence interval and precision of  $\pm 2.5\%$ .

### 3.7. Inclusion Criteria

- Patient  $\geq 18$  years old.
- Patients with baseline cancer pain that is adequately controlled with opioids.
- Presence of episodes of breakthrough pain associated with the cancer pain.
- Meeting the diagnostic criteria for breakthrough cancer pain (patient history and Portenoy's criteria) and the Davies algorithm.
- Patients who are not receiving treatment for breakthrough pain. It is not permitted the inclusion of patients receiving treatment for breakthrough cancer pain in order to avoid bias that may involve the treatment for the characterisation of breakthrough pain.
- Signing of the informed consent.

### 3.8. Exclusion Criteria

- No severe mental illness.
- Any medical condition or situation complicating the collection of study data as determined by the investigator is not permitted.

### 3.9. Study treatment

The patients participating in this cross-sectional, non-PAS, non-interventional study will not receive treatment in relation to the study aside from the treatment already prescribed by their usual physician.

## **4. STUDY POPULATIONS**

### **4.1. Definition of study populations to analyze**

**Prevalence Study Population:** To estimate the prevalence of breakthrough cancer pain will be used all data from patients collected in the prevalence form in the database.

**Characterization breakthrough pain Population (Secondary objectives Population):** All patients who meet the selection criteria and have given their informed consent will be included in the breakthrough pain characterization and quality of life study.

### **4.2. Disposition of subjects**

A flowchart will be provided to describe the total included patients in each part of analysis:

- To estimate the prevalence of breakthrough cancer pain.
- To characterize breakthrough pain.

Discrepancies between the numbers of patients of each part of analysis will be described by number of patient, site and the reason of the discrepancy.

### **4.3. Study Discontinuations**

Not applicable.

## 5. PREVALENCE STUDY RESULTS

### 5.1. General considerations

The prevalence study results will be performed in the “prevalence study population”.

As this is an epidemiological study, no imputation on the missing data will be calculated.

Valid percentages will be presented, that is, the real number of observations available in each variable will be used as the denominator. The number of missing data for each variable will be indicated.

### 5.1. Primary objective analysis

In the prevalence study the following variables will be collected:

- Patient with cancer pain: yes/no
- Breakthrough cancer pain: yes/no
- Diagnostic of BCP: Previously diagnosed; Diagnosed during the visit (according Davies algorithm)
- Date of visit.
- Age.
- Gender.
- Karnofsky PS (0 to 100).
- Type of tumour: head and neck, colorectal, esophagus, stomach, liver, leukemia, lymphoma, breast, multiple myeloma, bone and muscular, ovarian, pancreas, prostate, lung, kidney, central nervous system, testicle, uterus, bladder and other).
- Stage (I-IV).

The prevalence of breakthrough cancer pain and corresponding 95% confidence interval (95%CI) will be calculated as the percentage of subjects presenting breakthrough pain among patients with cancer pain controlled with opioids, collected by all investigators over one month.

#### Formula:

Prevalence of breakthrough cancer pain (%) = [Number of patients with breakthrough cancer pain / total number of patients registered with cancer pain] x 100.

The estimated annual prevalence will be calculated relative to the population of cancer patients with or without pain seen over one month.

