**Objectives**

To determine the prevalence of breakthrough cancer pain in an unselected, representative cohort of oncology outpatients with pain that is controlled with opioids.

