**Time (if cross-sectional) or Duration of data collection per subject**

Investigator will collect the study data in a single visit.

**Criteria for evaluation**Population descriptors

The primary assessment variable is the prevalence of breakthrough pain in patients with cancer pain controlled with opioids.

Demographic data and information relating to the characteristics of the cancer will be collected from all patients.

The characterisation of breakthrough pain will be carried out using the information collected in the tools used for the clinical assessment of the breakthrough pain:

- Alberta Breakthrough Pain Tool
- BPI questionnaire and
- Numerical Rating Scale for the assessment of pain intensity

To assess the quality of life of patients, we will use: SF-12 Questionnaire and Karnofsky performance status.

Main outcome variables

The primary assessment variable is the prevalence of breakthrough pain in patients with cancer pain controlled with opioids. All patients who attend pain consultations with cancer pain during 1 month will be used to determine the prevalence of breakthrough pain.

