### **Statistical methods**

The incidence/prevalence of breakthrough cancer pain and corresponding 95% confidence interval will be calculated as the percentage of subjects presenting breakthrough pain among patients with cancer pain controlled with opioids, collected by each investigator over one month.

The incidence/prevalence of breakthrough cancer pain and corresponding 95% confidence interval will also be calculated relative to the number of cancer patients collected.

The statistical methodology used will be based primarily on an exploratory analysis of the data through the calculation of descriptive parameters.

A descriptive analysis of the study variables will be carried out and the values of the continuous variables will be summarised in a table showing the mean, median, standard deviation and maximum-minimum range for each. The categorical variables will be presented as absolute frequencies and percentages.

The assessment of breakthrough pain intensity will be performed using the scores obtained on the numerical rating scale. A description of the scores will be given using the mean, median, standard deviation, maximum and minimum.

Each of the items on the BPI questionnaire and Alberta scale will be described, using the mean, median, standard deviation and range to describe the continuous variables and frequency distributions and percentages to describe the categorical variables.

The SF-12 quality of life scale scores will be given using the mean, median, standard deviation and range.

Breakthrough pain in patients with cancer pain will be characterised based on aetiology and pathogenesis, as well as other clinical characteristics. Continuous variables will be summarised showing the mean, median, standard deviation and maximum-minimum range for each and categorical variables will be presented as absolute frequencies and percentages.

The quality of life of patients with breakthrough cancer pain will be analysed based on its possible relationship with demographic characteristics and other clinically significant variables related to the cancer or to the breakthrough pain such as aetiology, frequency of episodes, pain intensity, time until peak of pain, crisis duration, cause, etc.

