### **3 Study Objective(s)**

#### **Primary objective**

- To estimate the prevalence of breakthrough cancer pain in an unselected representative cohort of cancer outpatients with or without pain who attend consultations at Medical Oncology, Hematology, Radiotherapeutic Oncology Departments, Pain Units and Palliative Care Units at participating sites. The estimated annual prevalence will be calculated relative to the population of cancer patients with or without pain seen in participating practices over one month.

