**BCP type IV graph:**

This graph represents BCP that starts gradually, reaches a maximum peak and is maintained for a period, before gradually decreasing.

The fundamental exposure factor in this study is patients with cancer who attend consultation at in Medical Oncology, Hematology, Radiotherapeutic Oncology Departments, Pain Units and Palliative Care Units with cancer pain controlled with opioids. Using patients' medical history and the Davies diagnostic algorithm [3], the investigator will confirm the presence of breakthrough pain. Those patients who agree to participate in the study to characterise breakthrough pain by signing the informed consent will be questioned on the other study variables and asked to complete the corresponding questionnaires.

All study data will be collected during the visit in which the patient signs the informed consent.

The data detailed below will be collected in relation to the study objectives:

- The primary assessment variable is the prevalence of breakthrough pain in patients with cancer pain controlled with opioids who attend consultations in Medical Oncology, Hematology and Radiotherapeutic Oncology Departments or Pain and Palliative Care Units for any reason.

Breakthrough pain is understood as the temporary exacerbation of pain occurring either spontaneously or in relation to a specific, predictable or unpredictable trigger in spite of relatively stable and adequately controlled baseline pain.

For a period of one month, each investigator will identify patients with cancer pain being treated with opioids who attend consultations, using the patient's medical history and the Davies diagnostic algorithm [3] to confirm the presence of breakthrough pain.

The investigator will continue collecting information from patients to estimate the prevalence for a month, regardless of whether the investigator recruited the 10 assigned patients (5 in pain units) for the characterization of breakthrough pain before.

- The prevalence of breakthrough pain in patients with cancer who attend consultations in Medical Oncology, Hematology, Radiotherapeutic Oncology Departments, Pain Units and Palliative Care Units for any reason over one month will also be determined.

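### The primary prevalence has inconsistent denominators: the SAP 5.1 formula divides by registered cancer pain, its own sentence says opioid-controlled pain, and the primary objective says cancer outpatients with or without pain

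*SAP*

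**What the plan says.** Three nested populations serve as the base of the primary prevalence.

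- **A, all cancer outpatients.** SAP 3.5 states the primary objective as "To estimate the prevalence of breakthrough cancer pain in an unselected representative cohort of cancer outpatients with or without pain", and Protocol section 3 has the same objective. It adds: "The estimated annual prevalence will be calculated relative to the population of cancer patients with or without pain seen in participating practices over one month". SAP 5.1 repeats that annual-prevalence sentence directly after its formula, but gives no formula or confidence interval for it there. The formula over all registered cancer patients, with a 95% CI, stands in SAP 5.2 under secondary analysis.
- **B, cancer pain.** The only formula in SAP 5.1 is "Number of patients with breakthrough cancer pain / total number of patients registered with cancer pain] x 100". It has support elsewhere. The Protocol Summary says "All patients who attend pain consultations with cancer pain during 1 month will be used to determine the prevalence of breakthrough pain", Protocol 10.1 has a near-identical sentence, Protocol 6.3 describes the study population as patients with cancer pain, and the new-cases formula in SAP 5.2 uses the same base.
- **C, cancer pain controlled with opioids.** The sentence above the SAP 5.1 formula says the prevalence is "calculated as the percentage of subjects presenting breakthrough pain among patients with cancer pain controlled with opioids, collected by all investigators over one month". The Protocol Summary objective reads "To determine the prevalence of breakthrough cancer pain in an unselected, representative cohort of oncology outpatients with pain that is controlled with opioids", and Protocol section 7 says "The primary assessment variable is the prevalence of breakthrough pain in patients with cancer pain controlled with opioids who attend consultations". The methods text in the Summary and in Protocol 10.1 agrees.

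The rules on whom to register differ too. Protocol 6.3 has investigators identify cancer patients. The opening of section 7 has pain patients on third-step opioids. The visit description in section 7 and Protocol 10.1 have opioid-treated pain patients.

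**The concern.** In a study whose primary purpose is to estimate a prevalence, the denominator defines the quantity. Here the sentence, the formula and the objective of the primary analysis name three different ones. Followed as written, the plan yields a percentage described as applying to opioid-controlled pain, computed over a group that may include pain patients without opioids or with uncontrolled baseline pain.

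Six subgroup results in SAP 5.2 (gender, age, specialty, Karnofsky, tumour type, stage) are tagged as the primary-objective prevalence and inherit the ambiguity. The ±1% precision is given once, without saying which denominator it belongs to.

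**Working it through.** **Can each quantity be computed from the listed variables?** Protocol section 7 lists pain, breakthrough pain, age, sex, Karnofsky, tumour type and stage, and adds when breakthrough pain was diagnosed. SAP 5.1 lists the same items plus visit date. B needs pain yes/no, which is listed. A needs every cancer patient to be registered, which holds under Protocol 6.3 but not under the opioid-treated rules. C needs opioid use and baseline control, and neither is listed.

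**Sentence against formula (C against B).** Let q be the share of registered pain patients who are opioid-controlled, c the prevalence among them and r the prevalence among the other pain patients. The formula returns q·c + (1 − q)·r.

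- If all cases lie within C (r = 0), it returns q·c. With c = 50% and assumed q of 0.5, 0.7 and 0.9, that is 25%, 35% and 45%.
- If q = 1, because only opioid-controlled patients were registered, the gap is zero. It may be near zero if only opioid-treated pain patients were registered.
- If r = c, the gap is zero whatever q is.

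The documents give neither q nor r. One definition in Protocol section 2 ties breakthrough cancer pain to opioid treatment, which points to r = 0. The definition in section 7 asks only for controlled baseline pain.

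**The plan's own precision.** Protocol 10.3: 200 × 66 = 13,200 patients, 50% prevalence, 95% CI, ±1%. Half-width = 1.96·√(p(1 − p)/n).

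- n = 13,200: 1.96·√(0.25/13,200) = 0.85 points, consistent with the stated ±1%.
- n needed for ±1.0: 1.96²·0.25/0.01² = 9,604, and 9,604/13,200 = 73%.

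The 200 per site is built on attendance for cancer, so the 13,200 belongs to A.

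**Precision under the SAP 5.1 formula (B).** Protocol section 2 gives pain in 18% to 62% of outpatients; applying this here is an assumption.

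- 18%: n = 2,376, half-width 2.01 points.
- 62%: n = 8,184, half-width 1.08 points.

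The share may be higher in Pain Units. The recruitment targets in Protocol section 7 (120 per specialty, 60 in hematology; 10 per investigator, 5 in Pain Units) imply 24 Pain Units: 3 × 12 + 6 + 24 = 66. Suppose every Pain Unit patient has pain and the other 42 sites (8,400 patients) follow 18% to 62%.

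- 200 per Pain Unit: n = 4,800 + 1,512 = 6,312 to 4,800 + 5,208 = 10,008, half-width 1.23 to 0.98.
- 100 per Pain Unit, in line with the lower attendance stated there: n = 2,400 + 1,512 = 3,912 to 2,400 + 5,208 = 7,608, half-width 1.57 to 1.12.

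**Precision under C.** n = 13,200 × pain share × q runs from 1,188 (18%, q = 0.5) to 7,366 (62%, q = 0.9), half-width 2.84 to 1.14.

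**Which population does the 50% fit?** With 50% among pain patients, the all-cancer figure is 0.50 × 0.18 = 9% to 0.50 × 0.62 = 31%. For 50% of all cancer patients, 0.50/0.62 = 81% of pain patients would need breakthrough pain at a 62% pain share, and at 18% it is impossible. Protocol section 2 also cites 33% to 37% in oncology outpatients, above that 9% to 31%. Read over all outpatients, it is compatible with 50% among pain patients only at a pain share of 0.33/0.50 = 66% to 0.37/0.50 = 74%.

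**The case against.** The study is descriptive, no test depends on the denominator, and the cancer-pain and all-cancer percentages both have explicit formulas and intervals. SAP 5.1 contains a single formula, so the subgroup results can be computed. If sites followed the opioid-treated instructions in Protocol section 7, patients registered with cancer pain would be nearly the group named in the sentence. The prevalence form is not in the documents and the SAP table index is blacked out, so an opioid item or a correct table title may exist. At a 62% pain share, ±1.08 rounds to the stated ±1%.

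Much of this stands and limits the point. It does not remove it. If only opioid-treated pain patients were registered, the all-cancer result named in the primary objective could not be produced, and being treated with opioids is not the same as being controlled on them. So the reading that closes one gap opens another.

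A reader might infer three stronger things that the documents do not support.

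- That the all-cancer prevalence is planned only as a secondary result. SAP 5.1 itself puts an annual prevalence on that population; what it lacks there is a formula and an interval.
- That the formula must understate the opioid-controlled prevalence. This needs r = 0, which follows from one protocol definition and not from the other.
- That sites built different registers. The differing instructions make this a risk; nothing shows that it happened.

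**Conclusion.** The inconsistency stands on the text: the sentence, the formula and the primary objective use different denominators, and the one in the sentence cannot be built from the listed variables.

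The size of the label error is unknown. It runs from near zero to a halving at q = 0.5, under assumed q and with all cases among opioid-controlled patients. The precision statement is firmer: ±0.85 belongs to all 13,200 attendees, and the SAP 5.1 formula gives about ±2.0 to ±1.1 at the cited pain shares, reaching ±1.0 only if about 73% of attendees have pain. That shortfall is small at the upper end and clear at the lower end.

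The documents do not settle which denominator should lead. The section 3 objective and the attendance-based 13,200 point to all cancer patients; the primary variable points to pain patients. The 50% assumption fits pain patients better at the cited pain shares, but the 33% to 37% figure has to be weighed as well. This should be fixed because it decides the headline figure, its name and its stated precision; it does not invalidate the planned results.

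**What to change.** In a revised SAP, before completion of data collection as Protocol section 10 requires, and documented as decided without sight of results:

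1. Describe the SAP 5.1 result as the prevalence among patients registered with cancer pain, unless the prevalence form does capture opioid use and baseline control.
2. Have the sponsor name one primary denominator with a reason, put its formula and 95% CI in SAP 5.1, label the other result secondary, and tie the six subgroup results in SAP 5.2 to the named one.
3. Replace the single ±1% with the precision for that denominator, stating the assumed pain share where it matters.
4. Report by site which patients were registered: all cancer, cancer pain, or opioid-treated pain.

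The SAP changes need no extra patients; the price is a less favourable precision figure if pain patients are primary. The SAP alone cannot finish step 2, because the section 3 objective conflicts with the Summary objective and the primary variable. Reconciling them is a protocol amendment affecting objectives, which under Protocol 5.1 needs a new ethics committee evaluation and administrative authorisation. Recruitment was scheduled from September 2016 to June 2017 and SAP version 2.0 is dated 24 January 2017, so the schedule left time. New form items may come too late at sites whose prevalence month has closed; there, relabelling is the realistic remedy.
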